## **9 Data analysis**

The data will be analyzed by Novartis and/or a designated CRO. Any data analysis carried out independently by the investigator should be submitted to Novartis before publication or presentation.

It is planned that the data from all centers that participate in this protocol will be used, so that an adequate number of patients will be available for analysis.

Data analyses will be presented by treatment regimen. Efficacy and safety data will be presented by the following treatment groups:

- Secukinumab 300 mg s.c. in combination with 26-week prednisolone taper regimen
- Placebo in combination with 26-week prednisolone taper regimen

The analysis will be conducted on all patient data at the time the trial ends. Any data analysis carried out independently by the investigator should be submitted to Novartis before publication or presentation.

### **9.1 Analysis sets**

The Randomized Analysis Set (RAS) consists of all randomized patients. Unless otherwise specified, mis-randomized patients will be excluded from the randomized set.

(Misrandomized patients are defined as cases where subjects were mistakenly randomized by the investigator/qualified site staff either prematurely or inappropriately prior to confirmation of the subject's final randomization eligibility and double-blind treatment was not

administered to the subject. If subjects were re-screened and successfully randomized they will be included in the RAS according to the treatment assigned in the last randomization.)

The Full Analysis Set (FAS) comprises all patients to whom study treatment has been assigned by randomization and who received at least one dose of randomized study treatment (secukinumab or placebo). According to the intent to treat principle, patients will be analyzed according to the treatment assigned to at randomization procedure.

The Safety Set includes all patients who received at least one dose of study treatment (secukinumab or placebo). Patients will be analyzed according to the study treatment received, where treatment received is defined as the treatment the patient received on the first day of study treatment.

## **9.2 Patient demographics and other baseline characteristics**

Demographic and other Baseline data including disease characteristics will be listed and summarized descriptively overall and by treatment group for the RAS.

Categorical data will be presented as frequencies and percentages. For continuous data, mean, standard deviation, median, minimum, and maximum will be presented. For selected parameters, 25th and 75th percentiles will also be presented.

Relevant medical histories and current medical conditions at Baseline will be summarized combined by system organ class and preferred term, by treatment group.

## **9.3 Treatments**

The Safety Set will be used for the analyses below. Categorical data will be summarized as frequencies and percentages. For continuous data, mean, standard deviation, median, 25th and 75th percentiles, minimum, and maximum will be presented.

The number of secukinumab and placebo injections received will be presented by treatment group.

The duration of exposure in weeks to secukinumab and placebo, actual cumulative dose and dose intensity (computed as the ratio of actual cumulative dose received and actual duration of exposure) will be summarized by means of descriptive statistics using the Safety Set.

Prior medications are defined as treatments taken and stopped prior to first dose of study treatment. Any medication given at least once between the day of first dose of randomized study treatment and the date of the last study visit will be a concomitant medication, including those which were started pre-baseline and continued into the period where study treatment is administered.

Concomitant medications and significant non-drug therapies prior to and after the start of the study treatment will be listed and summarized according to the Anatomical Therapeutic Chemical (ATC) classification system, by treatment group.

## 9.4 Analysis of the primary variable

### 9.4.1 Primary variable

The primary endpoint is the proportion of GCA patients who adhere to the prednisolone taper regimen and are in sustained remission until Week 28.

The analysis of the primary variable will be based on the following estimand:

- Analysis set: FAS
- Variable of interest: Proportion of GCA patients who adhere to the prednisolone taper regimen and are in sustained remission until Week 28 (refer to Table 2-1 for sustained remission definition)
- Intervention effect: Effect between secukinumab versus placebo at Week 28 regardless of adherence to randomized treatment.
- Summary measure: Odds ratio (OR)

### 9.4.2 Statistical model, hypothesis, and method of analysis

A binomial distribution will be assumed for the observed data from this study. Due to the conjugate nature of the Beta distributions, the posterior distributions for the sustained remission response rates until Week 28 for secukinumab and placebo will also be Beta distributions.

The response rate of the comparable placebo-arm of the GIACTA study (Stone et al 2017) will be used as the prior distribution for the placebo response rate for the primary endpoint in this study. The parameters of this Beta distribution are 10 and 43, i.e. Beta (10, 43). The prior distribution for the response rate on secukinumab will be a Beta distribution with parameters 1/2 and 1/2, i.e. Beta (1/2, 1/2). This prior distribution was chosen because it has low weight to reflect the lack of current knowledge on the response rate on secukinumab in GCA.

Posterior distributions for the estimate of the OR, risk-ratio (RR) and risk difference (RD) will be derived by sampling from the posterior distributions of the response rates of secukinumab and placebo. The associated median and 95% credibility interval will be presented. In addition the probability of the posterior distribution of the OR of the comparison of secukinumab versus placebo being greater than 1 will be provided.

The posterior median OR will be calculated such that the OR is in favor of secukinumab. The probability of the posterior distribution of the OR of the comparison of secukinumab versus placebo being greater than 1 will be provided.

Furthermore, the proportion of patients in sustained remission until Week 28 will be summarized descriptively by treatment group.

### 9.4.3 Handling of missing values/censoring/discontinuations

Patients who (1) do not achieve remission within 12 weeks of Baseline; or (2) are in the “escape arm”; or (3) drop out from the study prior to/on Week 28, or (4) do not have information to evaluate sustained remission response at Week 28, will be classified as non-responders in the primary analysis. Patients receiving less than the full amount of

prednisolone as required by the taper, e.g. due to missing tablets, will not be classified as non-responders.

#### **9.4.4 Sensitivity analyses**

In order to assess the robustness of the primary endpoint, sensitivity analyses are planned. These may include, but are not limited to:

- Using a non-informative prior, i.e. uniform prior Beta (1/2, 1/2), for both treatment groups
- Evaluating the primary endpoint using a chi-square test to see if there is an association between the primary endpoint and treatment. In addition, the OR, RD, and RR will be presented.

Furthermore, the primary analysis will be repeated based on only signs and symptoms of GCA (refer to [Section 6.3.1.1](#) for definition) in order to mitigate against the possibility of biasing.

#### **9.4.5 Subgroup analyses**

Subgroup analyses of the primary endpoint will be performed:

- To investigate the difference between new-onset (diagnosed within 6 weeks of baseline) and refractory patients (diagnosed  $\geq$  6 weeks before baseline and previous treatment with  $\geq 25$  mg/day prednisolone for  $\geq 2$  consecutive weeks) given the homogenous nature of the disease.
- To allow assessment of the benefit/risk of secukinumab in patients who need a higher ( $> 40$  mg/day) versus lower ( $\leq 40$  mg/day) initial dose of prednisone will also be provided.

The posterior distributions for the estimate of the RD, OR, and RR will be derived and the associated median and 95% credibility interval will be presented.

### **9.5 Analysis of secondary variables**

#### **9.5.1 Efficacy variables**

The following secondary efficacy endpoints for this study will be analyzed for the FAS:

- Remission rate at Week 12
- Time to first GCA flare after remission (up to Week 52)
- Total cumulative prednisolone dose over 28 Weeks and 52 Weeks
- Proportion of GCA patients in sustained remission at Week 52
  - Definition of remission: absence of flare.
  - Definition of sustained remission: patients without flare until Week 52 and in adherence to the protocol prednisolone taper regimen + prednisolone-free phase from Week 27 onwards
  - Definition of flare: determined by the investigator and defined as the recurrence after remission of signs or symptoms of GCA and/or erythrocyte sedimentation rate (ESR)  $\geq 30$  mm/hr and/or CRP  $\geq 10$  mg/L attributable to GCA
- Proportion of patients on prednisolone dose  $\leq 5$  mg/day at Week 19, Week 28 and Week 52

- Change from Baseline PGA at Week 4, 8, 12, 16, 20, 24, 28, 36, 44 and 52
- Change from Baseline PhGA at Week 4, 8, 12, 16, 20, 24, 28, 36, 44 and 52
- Change from Baseline FACIT-Fatigue at Week 4, 8, 12, 16, 20, 24, 28, 36, 44 and 52
- Change from Baseline SF-36 at Week 4, 8, 12, 16, 20, 24, 28, 36, 44 and 52
- Change from Baseline EQ-5D at Week 4, 8, 12, 16, 20, 24, 28, 36, 44 and 52
- Change from Baseline CRP at Week 4, 8, 12, 16, 20, 24, 28, 32, 36, 40, 44, 48 and 52
- Change from Baseline ESR at Week 4, 8, 12, 16, 20, 24, 28, 32, 36, 40, 44, 48 and 52

Similar to the primary endpoint methodology, the posterior distributions for the estimate of the OR, RD, and RR will be derived by sampling from the posterior distributions of the remission response rates at Week 12 of secukinumab and placebo. The prior distribution for the remission response rates at Week 12 for both treatment groups will be a Beta distribution with parameters 1/2 and 1/2, i.e. Beta (1/2, 1/2). The associated median and 95% credibility interval will be presented. Patients that withdrew from the study or entered “escape” therapy will be classified as non-responders from the point of withdrawal/escape onwards. Patients with a missing remission status at a particular time point will be classified as non-responders at that time point. In addition, the proportion of patients in remission over time will be summarized descriptively by visit and by treatment group.

The time to first GCA flare after remission (up to Week 52) will be summarized using Kaplan Meier curves. Patients who:

- Withdraw from the study prior to Week 52 will be censored at the time of withdrawal
- Do not have a flare up to Week 52 will be censored at Week 52

Descriptive statistics will also be provided for time to first GCA flare after clinical remission (up to Week 52).

Total cumulative prednisolone dose over 28 and 52 weeks will be summarized over time by treatment group.

The proportion of GCA patients in sustained remission at Week 52 will be analyzed using the methods outlined in Section 9.4.2. Patients who (1) do not achieve remission within 12 weeks of Baseline; or (2) are in the “escape arm”; or (3) drop out from the study prior to/on Week 52, or (4) do not have information to evaluate sustained remission response at Week 52, will be classified as non responders. Patients receiving less than the full amount of prednisolone as required by the taper, e.g. due to missing tablets, will not be classified as non-responders.

The number (and percentage) of patients on prednisolone dose  $\leq$ 5mg/day at Week 19, 28 and 52 will be summarized by treatment group.

The continuous secondary efficacy endpoints (actual value and change from baseline value) will be summarized descriptively by visit (where applicable) and by treatment group.

For SF-36, the following variables will be evaluated:

- SF-36 domain scores

- SF-36 domain score responders
  - Type I responders (improvement of  $\geq 5$  points in  $\geq 6$  domains)
  - Type II responders (improvement of  $\geq 10$  points in  $\geq 3$  domains)
- SF-36 PCS and MCS scores
- SF-36 PCS and MCS score responders
  - Type I responders (improvement of  $\geq 2.5$  points)
  - Type II responders (improvement of  $\geq 5$  points)

The EQ-5D is a questionnaire with 5 questions (regarding mobility, self-care, usual activities, pain/discomfort, and anxiety/depression) each with three categories (no problem, moderate problem, severe problems) and a health state assessment from 0 (worst possible health state) to 100 (best possible health state) (see [Section 6.5.2.1.4](#) for further details). The number and percentage of subjects in each of the three categories for each question will be presented by visit and treatment group. Summary statistics will be provided for the health state assessment by visit and treatment group.

### **9.5.2 Safety variables**

For all safety analyses, the Safety Set will be used. All listings and tables will be presented by treatment group.

Safety summaries (tables, figures) include only data from the on-treatment period with the exception of Baseline data which will also be summarized where appropriate (e.g. change from Baseline summaries). In addition, a separate summary for death including on treatment and post treatment deaths will be provided. In particular, summary tables for AEs will summarize only on-treatment events, with a start date during the on-treatment period (treatment-emergent AEs).

Treatment-emergent AEs are defined as events which start after the first dose of study medication or events present prior to the first dose of study medication but increase in severity after dosing based on preferred term and within last dose + 20 weeks.

### **Adverse events**

All information obtained on AEs will be displayed by treatment group and patient.

The number (and percentage) of patients with treatment-emergent AEs will be summarized in the following ways:

- By treatment group, primary system organ class and preferred term.
- By treatment group, primary system organ class, preferred term and maximum severity.

Separate summaries will be provided for study medication related AEs, death, serious AEs, other significant AEs leading to discontinuation.

A patient with multiple AEs within a primary system organ class is only counted once towards the total of the primary system organ class.

## **Vital signs**

All vital signs data will be listed by treatment group, patient, and visit/time and if ranges are available, abnormalities will be flagged.

Summary statistics will be provided by visit and by treatment group. Change from baseline will only be summarized for patients with both baseline and post-baseline values.

## **Clinical laboratory evaluations**

All laboratory data will be listed by treatment group, patient, and visit and if normal ranges are available abnormalities will be flagged.

Summary statistics will be provided by treatment and visit. Change from baseline will only be summarized for patients with both baseline and post-baseline values.

Shift tables using the low/normal/high/ (low and high) classification will be used to compare Baseline to the worst on-treatment value.

## **Other safety evaluations**

### **Immunogenicity**

All immunogenicity results (Anti-AIN457 antibodies) will be listed by treatment group, patient and visit.

### **QuantiFERON TB-Plus test**

All QuantiFERON TB-Plus test results will be listed by treatment group, patient and visit.

### **9.5.3 Resource utilization**

Not applicable.

## 9.5.6 Biomarkers

Not applicable.

## 9.8 Sample size calculation

Based on the observed response rates in the GIACTA study (Stone et al 2017), there were 56 out of 100 patients on tocilizumab every other week (56%) in combination with 26-week prednisolone taper regimen and 9 out of 51 patients treated with placebo (18%) in combination with 52-week prednisolone taper regimen. The expected observed responders in a sample size of 25 patients per treatment group is then  $25*(56/100) = 14$  and  $25*(9/51) = 4$ . The posterior distribution of the expected difference in proportions was investigated for the sample size of 25 patients per treatment group.

Using an uninformative prior Beta (1, 1) for the secukinumab group and an informative prior for the expected observed responders in the placebo group of Beta (10, 43), 10000 Monte Carlo simulations of each posterior density was then computed and the posterior distribution of the difference then described using the 2.5, 50 (median) and 97.5 percentiles (Table 9-1).

Other plausible outcomes have been investigated if the observed response rates are different from expected (refer to Table 9-1).

**Table 9-1 Sensitivity to changes in assumptions in observed response rates**

Observed response rate	Secukinumab (p1)	Placebo (p2)	Posterior quantiles			Posterior Prob(p1 > p2)
			2.5%	Median	97.5%	
	0.56	0.16	0.19	0.38	0.56	0.99
	0.56	0.20	0.16	0.36	0.55	0.99
	0.56	0.24	0.15	0.35	0.55	0.99
	0.56	0.28	0.13	0.34	0.54	0.99
	0.52	0.16	0.14	0.34	0.53	0.99
	0.48	0.16	0.11	0.31	0.51	0.99

## 10 Ethical considerations

### 10.1 Regulatory and ethical compliance

This clinical study was designed and shall be implemented, executed and reported in accordance with the ICH Harmonized Tripartite Guidelines for Good Clinical Practice, with applicable local regulations (including European Directive 2001/20/EC, US CFR 21, and Japanese Ministry of Health, Labor, and Welfare), and with the ethical principles laid down in the Declaration of Helsinki.

## 10.2 Informed consent procedures

Eligible patients may only be included in the study after providing (witnessed, where required by law or regulation), IRB/IEC-approved informed consent. Informed consent must be obtained before conducting any study-specific procedures (e.g. all of the procedures described in the protocol). The process of obtaining informed consent must be documented in the patient source documents.

Novartis will provide to investigators in a separate document a proposed ICF that complies with the ICH GCP guideline and regulatory requirements and is considered appropriate for this study. Any changes to the proposed consent form suggested by the investigator must be agreed to by Novartis before submission to the IRB/IEC, and a copy of the approved version must be provided to the Novartis monitor after IRB/IEC approval.

Women of child bearing potential must be informed that taking the study treatment may involve unknown risks to the fetus if pregnancy were to occur during the study and agree that in order to participate in the study they must adhere to the contraception requirement for the duration of the study. If there is any question that the patient will not reliably comply, they must not be entered in the study.

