### 3 Investigational plan

#### 3.1 Study design

This randomized, parallel-group, double-blind, placebo-controlled, multicenter, Phase II study is designed to evaluate the efficacy of secukinumab compared to placebo in combination with a 26-week prednisolone taper regimen in terms of sustained remission in patients with newly diagnosed or relapsing GCA who are naïve to biological therapy.

The study will consist of 6-week (maximum duration) screening period, a 52-week treatment period and a 8-week safety follow-up period (Figure 3-1). Patients who do not achieve remission by Week 12, experience a flare after remission or cannot adhere (as described below) to the prednisolone taper regimen will enter “escape”. Upon entering “escape”, patients will receive prednisolone at a dose determined by the physician’s clinical judgment and continue to receive secukinumab or placebo in a blinded manner. Patients in “escape” should continue to attend all subsequent scheduled visit assessments.

Patients who have received an additional corticosteroid as stated in the taper regimen will be considered as not having adhered to the protocol-defined prednisolone taper regimen. Patients not adhering to the prednisolone taper will be classified as non-responders in the primary analysis, regardless of their status of sustained remission. Patients receiving less than the full amount of prednisolone as required by the taper (due to missing tablets) will not be classified as non-responders, unless other non-response criteria are fulfilled.

**Screening period:** During the screening period, patients may receive glucocorticoids for the treatment of GCA at the discretion of the investigator. By the end of the screening period patients should be able to switch to the Sponsor-provided prednisolone in order to follow the protocol-defined prednisolone tapering regimens.

**Randomization:** Patients will be assigned to one of the following 2 arms in a 1:1 ratio:

[figure not shown]
- Group 1: secukinumab 300 mg s.c. + 26-week prednisolone taper regimen
- Group 2: placebo s.c. + 26-week prednisolone taper regimen

Patients will receive secukinumab/placebo at Baseline, Week 1, 2, 3, 4, then every 4 weeks thereafter through to Week 48 (last dose) at the study center. Assessments will be performed in accordance to the study schedule. Patients in both groups will follow the protocol-defined prednisolone taper regimen.

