At every visit, each patient's disease activity and condition will be assessed in order to determine whether the patient can adhere to the defined prednisolone taper regimen (open-label fashion). If they cannot adhere to the taper regimen or are experiencing a flare (definition above), they must enter the "escape" arm and receive prednisolone at a dose determined by the physician based on clinical need and will continue to receive secukinumab 300 mg or placebo s.c. (still blinded).

Safety evaluation will be included in all visits including two safety follow-up visits performed 8 and 12 weeks after the last study drug administration at Week 48 (this will be at Week 56 and Week 60 for patients completing the study according to the protocol).

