Women of child bearing potential must be informed that taking the study treatment may involve unknown risks to the fetus if pregnancy were to occur during the study, and agree that in order to participate in the study they must adhere to the contraception requirements outlined in [Section 4.2](#) (Exclusion criteria). If there is any question that the patient will not reliably comply, they should not be entered or continue in the study.

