#### **4.2 Exclusion criteria**

Patients who fulfill **any** of the following criteria are not eligible for inclusion in this study:

1. Pregnant or nursing (lactating) women where pregnancy is defined as the state of a female after conception and until the termination of gestation, confirmed by a positive human chorionic gonadotropin (hCG) laboratory test.

2. Women of childbearing potential, defined as all women physiologically capable of becoming pregnant, unless they are using effective methods of contraception during dosing of study treatment and for a minimum of 20 weeks after the last dose of secukinumab. Effective contraception methods include:
  - Total abstinence (when this is in line with the preferred and usual lifestyle of the patient. Periodic abstinence (e.g. calendar, ovulation, symptothermal, post-ovulation methods) and withdrawal are not acceptable methods of contraception.
  - Female sterilization (have had surgical bilateral oophorectomy with or without hysterectomy), total hysterectomy or tubal ligation at least 6 weeks before taking investigational drug. In case of oophorectomy alone, only when the reproductive status of the woman has been confirmed by follow-up hormone level assessment.
  - Male sterilization (at least 6 months prior to screening). For female patients on the study, the vasectomized male partner should be the sole partner for that patient
  - Barrier methods of contraception: Condom or Occlusive cap (diaphragm or cervical/vault caps).
  - Use of oral, (estrogen and progesterone), injected or implanted hormonal methods of contraception or other forms of hormonal contraception that have comparable efficacy.

Women are considered post-menopausal and not of child bearing potential if they have had at least 12 months of natural (spontaneous) amenorrhea with an appropriate clinical profile (e.g. age appropriate, history of vasomotor symptoms) or have had surgical bilateral oophorectomy (with or without hysterectomy), total hysterectomy or tubal ligation at least 6 weeks ago. In the case of oophorectomy alone, only when the reproductive status of the woman has been confirmed by follow up hormone level assessment is she considered not of child bearing potential.

3. Previous exposure to secukinumab or other biologic drug directly targeting IL-17 or IL-17 receptor.

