## 5.6 Study completion and discontinuation

### 5.6.1 Study completion and post-study treatment

A subject will be considered to have completed the study when the subject has completed the last visit planned in the protocol. (i.e. 52-week treatment period, and 8-week follow-up period). As per the study design, patients who do not achieve remission by Week 12, experience a flare after remission or cannot adhere to the prednisolone taper regimen will enter “escape”. Upon entering “escape”, patients will receive prednisolone at a dose determined by the Investigator’s clinical judgment and continue to receive secukinumab or placebo in a blinded manner until Week 48. No further secukinumab treatment will be provided after Week 48. No further prednisolone treatment will be provided after Week 52.

Study completion is defined as when the last patient completes their End of Study Visit, and any repeat assessments associated with this visit have been documented and followed-up appropriately by the Investigator, or in the event of an early study termination decision, the date of that decision.

Normally, all randomized and/or treated patients should have a safety follow-up call conducted 60 days after last administration of study treatment; however, the 60 days falls within the study 8-week follow-up period, where no s.c. study treatment is given; therefore, the safety follow-up is part of the End of Study. As so far, no indication for an increased incidence or progression of malignancies was observed in clinical studies of secukinumab, no further monitoring after the two follow-up visits is required.

All SAEs reported during this time period must be reported as described in [Section 7.1.3](#).

After study participation, the patients will continue to be treated at the investigators discretion according to local practice. The investigator must provide follow-up medical care for all patients who prematurely withdraw from the study, or must refer them for appropriate ongoing care.

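### The consent section of the protocol (10.2) ties contraception to study duration, which on the visit schedule ends up to 8 weeks before the post-dose period in exclusion criterion 2

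*Protocol*

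**What the plan says.** Four places in the protocol bear on how long contraception must be used.

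- **Exclusion criterion 2** (Section 4.2, with the same wording in the protocol summary) excludes women of childbearing potential unless they use effective contraception during dosing and "for a minimum of 20 weeks after the last dose of secukinumab".
- **Section 10.2**, on informed consent, says what these women must be told and must agree to in order to take part, namely that "they must adhere to the contraception requirement for the duration of the study". It gives no cross-reference and no period after the last dose.
- **Section 3.6**, on risks and benefits, has a nearly identical sentence. There the women must "agree that in order to participate in the study they must adhere to the contraception requirements outlined in" Section 4.2, and no separate duration is given.

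The calendar comes from two further sections. Section 3.1 has dosing at Baseline and Weeks 1 to 4, "then every 4 weeks thereafter through to Week 48 (last dose) at the study center", followed by "two safety follow-up visits performed 8 and 12 weeks after the last study drug administration at Week 48". Section 5.6.1 defines completion by the last planned visit ("i.e. 52-week treatment period, and 8-week follow-up period").

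**The concern.** Section 10.2 is where the protocol states the undertaking that a woman gives at consent. Its time frame is the study, whereas criterion 2 counts from the last dose. If the study ends for a patient less than 20 weeks after her last dose, the undertaking described in Section 10.2 is shorter than the condition on which she was admitted.

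What is at stake is possible fetal exposure after the last visit. No scheduled contact after Week 60 would pick up a misunderstanding. Section 3.6 shows that the same sentence can be written without the difficulty, by pointing to Section 4.2. No endpoint, analysis or efficacy conclusion is affected.

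**Working it through.** **Inputs**

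- Last planned dose: Week 48 (Section 3.1).
- Last planned visit: Week 60 (Sections 3.1 and 5.6.1).
- Minimum period after the last dose in criterion 2: 20 weeks (Section 4.2 and protocol summary).
- Period in Section 10.2: the duration of the study.

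**Reproducing the plan's own calendar.** Section 5.6.1 gives 52 + 8 = Week 60. Section 3.1 places the two follow-up visits 8 and 12 weeks after Week 48: 48 + 8 = Week 56 and 48 + 12 = Week 60. The two agree. The SAP's safety observation period of 84 days after the last dose (Section 2.1.1.4) is 84 / 7 = 12 weeks, which matches as well.

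**Comparison for a patient dosed through Week 48**

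- Section 10.2, read alone: to Week 60, that is 60 − 48 = 12 weeks after the last dose.
- Criterion 2: to at least 48 + 20 = Week 68.
- Difference: 68 − 60 = 8 weeks.

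**Earlier last dose, with follow-up still running to Week 60.** Let L be the week of the last dose. The shortfall is max(0, L + 20 − 60).

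| Last dose (week) | Criterion 2 runs to at least week | Study ends at week | Shortfall (weeks) |
|---|---|---|---|
| 48 | 68 | 60 | 8 |
| 44 | 64 | 60 | 4 |
| 40 | 60 | 60 | 0 |
| 36 or earlier | 56 or earlier | 60 | 0 |

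**Alternative meaning of the study's end.** The glossary defines the end of the trial as the last visit of the last patient. Suppose a woman is dosed through Week 48 and her own Week 60 visit falls d weeks before that date. Her shortfall is then max(0, 8 − d): none if d is 8 or more, and still the full 8 weeks for the last patient.

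The table does not cover a woman who leaves the study before Week 60. For her, the length of the Section 10.2 period depends on what is meant by the duration of the study, which that section does not define.

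**The case against.** The strongest reply is that Section 10.2 sets no period of its own. It speaks of a contraception requirement as something already laid down, and criterion 2 is the only place where such a requirement is set out. The parallel sentence in Section 3.6 names Section 4.2 outright. On this view Section 10.2 is a loose paraphrase. Criterion 2 controls entry and appears twice, and a woman who follows it also satisfies Section 10.2. The protocol also uses 20 weeks after the last dose for adverse event monitoring (7.1.1) and SAE reporting (7.1.3), so an investigator is unlikely to read Section 10.2 as a new, shorter rule.

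Much of this stands, and it rules out three stronger readings that a reader might infer:

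- *Section 10.2 limits contraception to 12 weeks after the last dose.* It does not say so. The 12 weeks follow from the visit schedule, and the section contains no word such as only or until.
- *The two sections cannot both be obeyed.* They can, by following criterion 2.
- *Women are told the shorter period.* The documents do not show this. Section 10.2 is protocol text, and it says that the proposed consent form is supplied separately. That form was not available for review.

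What the reply does not remove is the added time frame. Section 3.6 leaves the duration to Section 4.2. Section 10.2 drops that reference and puts a different end point in its place. A reader who drafts or checks a consent form from Section 10.2 alone would find no mention of a period after the last dose.

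**Conclusion.** The inconsistency is real but minor. The undertaking in Section 10.2, read alone, ends earlier than criterion 2 requires. The difference is 8 weeks for a patient dosed through Week 48, 4 weeks for a last dose at Week 44, and nil for a last dose at Week 40 or earlier. These figures assume that the study ends for each patient at her own Week 60 visit, as Section 5.6.1 suggests, and that she is followed to that visit. Under the glossary's definition of the trial's end, some earlier-enrolled women would have a smaller gap or none, and the last patients would still have the full gap.

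Few women are likely to be affected, because inclusion criterion 3 requires an age of at least 50. The documents give no expected number. Whether any patient would actually be given the shorter period is unknown without the consent form. The point deserves correction because it concerns fetal exposure and the remedy is very cheap. It has no bearing on the trial's statistical conclusions.

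**What to change.** Reconcile Section 10.2, Section 3.6, exclusion criterion 2 in Section 4.2 and the same criterion in the protocol summary, so that all four state, or refer to, one and the same contraception period. The simplest edit is to have Section 10.2 cross-refer to Section 4.2, as Section 3.6 already does, in place of giving its own time frame. Then check that the consent form matches. Which period applies is for the sponsor to decide; this review does not propose one.

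The cost is one sentence in the protocol and a check of the consent form. No visit, assessment or analysis needs to change for the wording to be made consistent.
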